Methods: This pilot randomized controlled trial intends to include 30 stable COPD patients, who are psychologically distressed and will be randomly assigned to the intervention (appbased mindfulness + treatment as usual) and waitlist control (treatment as usual) condition. The intervention group will be introduced to the intervention in a face-to-face learning phase (single day) conducted by the study coordinator while being hospitalized. Patients in the intervention group will be instructed to practice mindfulness daily using at least one of 4 short exercises (10-15 minutes) over a period of 8 weeks, starting in the hospital and continuing at home. The exercises will be delivered by a software (movisensXS). Additionally, dyspnoea, stress, relaxation, affect and oxygen saturation (assessed by a pulse oximeter) will be assessed before and after each exercise via the software.

Questionnaire data will be collected equally in both groups at 5 measurements: baseline, after 4 weeks, after the intervention (8 weeks) and at follow-up (4 and 6 months). Physiological measures (heart rate variability, electrodermal activity, heart rate) will be conducted at the same 5 measurements, using an ecg and eda sensor (movisens EcgMove4, movisens EdaMove4). Physiological measures will be assessed during the conduction of a cognitive stress test (Stroop-test), as well as before and after the conduction (at rest). Hair cortisol will be collected at baseline, after the intervention (8 weeks) and at follow-up (4 and 6 months). Face-to-face exit interviews will be conducted in the intervention group after 8 weeks to further assess patients' experiences with the intervention.

The primary outcome measures are psychological distress and the intervention's feasibility. The secondary outcome parameters for immediate effects of mindfulness exercises will be dyspnoea, stress, relaxation, affect (anxiety, depression, happiness) and oxygen saturation. The secondary outcome parameters for intermediate and long-term effects are heart rate variability, electrodermal activity, heart rate, health-related quality of life, health status impairment, fatigue, breathlessness catastrophizing, perceived and chronic stress, mindfulness and self-compassion. Additionally, compliance regarding medication-intake, perception of exacerbations, frequency and intensity of exacerbations and hospitalization rate as well as patients' experiences with the intervention are assessed.

Klinik Ottakring

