intervention, as different exercises can be chosen based on patients' preferences and needs. Furthermore, mobile health is an emerging and promising field, which
is both economic and feasible when used in health care. In addition, as personalized medicine is a growing field of interest and holds great potential, the presented study aims to identify treatable traits and patients who benefit most from the intervention.
Finally, this study will examine the effects of mindfulness on

Finally, this study will examine the effects of mindfulness on psychophysiological stress markers (e.g. heart rate variability), which play an important role in COPD (Andreas, Haarmann, Klarner, Hasenfuß, & Raupach, 2014). It is well known that physiological and psychological stress symptoms can be reduced by MBIs (Pascoe et al., 2017). Yet, this effect has poorly been studied in COPD patients to date.

OBJECTIVES	Primary Research Questions
	• Is a brief digital mindfulness-based intervention feasible for stable COPD patients?

Klinik Ottakring

Klinik Floridsdorf

V

Wiener Gesundheitsverbund Klinik Floridsdorf

	• Can a brief digital mindfulness-based intervention reduce psychological distress in stable, but psychologically distressed, COPD patients (using the "Hospital Anxiety and Depression Scale")?
	Secondary Research Questions
	• What are the immediate effects of a short mindfulness exercise for stable COPD patients on dyspnea, acute perceived stress, relaxation, affect and oxygen saturation?
	• What are the effects of daily short mindfulness practice for stable COPD patients on patients' stress level and stress reactivity (heart rate variability, electrodermal activity), when being exposed to a cognitive stressor (Strooptest)?
	• What are the effects of daily short mindfulness practice for stable COPD patients on patients' dealing with the exposure to a cognitive stressor (Stroop-Test)? Are there effects on anxiety, panic, acute perceived stress, relaxation, affect and oxygen saturation?
	• What are the intermediate and long-term effects of daily short mindfulness practice for stable COPD patients on health-related quality of life, health status impairment, fatigue, breathlessness catastrophizing, perceived stress, mindfulness and self-compassion?
	 Does the compliance regarding medication differ between the groups due to the intervention?
	How do patients experience the intervention?

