	 How often do patients meditate by using the app? How long? When? Do they prefer a specific mindfulness exercise?
	• Which patients benefit the most from the intervention (moderating factors, e.g.
	 age)? Do mindfulness and self-compassion mediate the intermediate and long-term effects on psychological distress?
DESIGN / PHASE	 pilot and feasibility study randomized controlled trial including follow-up
	• two treatment arms: intervention + treatment as usual (TAU) vs. waitlist (TAU)
	 ecological momentary assessment (EMA) study ecological momentary intervention (EMI) study (app-based)
	 prospective and experimental
	mixed methods analysismulti-centred
	multi-centred
STUDY PLANNED DURATION	6 months (8 weeks intervention + follow-up)
CENTER(S)/	Respiratory unit of the "Klinik Ottakring", Vienna, Austria
COUNTRY(IES)	Respiratory unit of the "Klinik Floridsdorf", Vienna, Austria
PATIENTS /	Groups:
GROUPS	 Intervention group: mindfulness exercises + TAU Waitlist control group: TAU
	Sample size: 30 COPD patients (15 patients in each group)
L	

V

Wiener Gesundheitsverbund Klinik Floridsdorf

	Sampling method: screening of all eligible patients during survey period, inclusion of all eligible interested patients
	Blinding: single blinding (of assessors)
	Allocation: equal treatment allocation via block randomization
ETHICS	 patients' written informed consent pseudonymisation of patients: Patients' personal data is noted on 2 documents: the patients' information (name, birth date, code) and the patients' contact details (name, birth date, address, phone number, email address, code). These documents are safely stored in a locked cupboard in the Klinik Ottakring, Vienna, Austria. Only members of the research team have access to the cupboard's key. After the screening, the patient is given a unique reference code (continuous numerical code starting from 01). In the following, only this numerical code will be used to allocate the data to the patient. The allocation of the patients' personal data to their numerical code will only be possible using either the patients' information or the patients' contact details. pseudonymised data analysis provision of mindfulness intervention to waitlist control group after study completion examination and agreement by the ethics committee of the "Wiener Krankenanstaltenverbund", Vienna, Austria

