INCLUSION CRITERIA	 spirometry confirmed (FEV1 <80%) COPD diagnosis psychological distress (as assessed by the Hospital Anxiety and Depression Scale): HADS-A ≥ 8 OR HADS-D ≥ 8 OR HADS total score ≥ 16 age ≥ 40 years ability to understand German physical and mental capability to attend the intervention, judged by the treating physician life expectancy > 6 months as judged by treating physician ability to use a smartphone
EXCLUSION CRITERIA	 ability to use a smartphone auditory impairment active asthma diagnosis any other known severe comorbidities such as heart failure (LVF<35%), uncontrolled diabetes, concomitant cancer, stroke, unstable coronary heart disease, respiratory failure history of/current severe psychological disorder (e.g. schizophrenia, severe cognitive impairment) current acute exacerbation of COPD any other relevant acute health crisis interfering with the study intervention (e.g. Covid-19) receiving any psychosocial treatment (e.g. psychotherapy) regular other systematic mind-body-practice
STUDY PERIODS	Period 1: individual mindfulness practice at home (baseline - 8 weeks)
	Period 2: Follow-up (3 months and 6 months)

VV

Wiener Gesundheitsverbund Klinik Floridsdorf

MEASUREMENTS	Paper-pencil data collection (baseline, 4 weeks, 8 weeks, 4 months, 6 months) psychological distress, perceived stress, health related quality of life, health status impairment, fatigue, mindfulness, self-compassion, breathlessness catastrophizing
	Psychophysiological data collection (baseline, 4 weeks, 8 weeks, 4 months, 6 months): heart rate variability, electrodermal activity (before, during and after the conduction of a cognitive task (Stroop-test))
	EMA data collection (daily for intervention period of 8 weeks):
	 pre-meditation (event-based): dyspnea, acute perceived stress, relaxation anxiety, depression, happiness, oxygen saturation (pulse oximeter) post-meditation (event-based): dyspnea, acute perceived stress, relaxation anxiety, depression, happiness, oxygen saturation (pulse oximeter)
STUDY TIME-LINE	Recruitment:
	 pulmonary ambulances of the Klinik Ottakring and Klinik Floridsdorf previously hospitalized COPD patients in the Klinik Ottakring and Klinil Floridsdorf invitation to the intervention via telephone call or personal invitation in the pulmonary ambulance (flyer and oral information)
	• invitation to the intervention via posting a flyer on social media (Facebook)
	Telephone-Screening:
	screening for inclusion and exclusion criteria

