	Period 1 (patients' home)
	 Day 0: Informed consent Baseline data collection Sociodemographic and medical data Paper-pencil data collection Chronic stress (collection of hair sample) Psychophysiological data collection
	Day 1:
	 Introductory and learning phase (face-to-face) Installation and testing of app, explanation of intervention, conduction of al mindfulness exercises in the presence of study investigator From now on: Individual daily meditation + daily EMA data collection Possibility of consulting the study coordinator in person and if necessary discussing/solving problems in period 1
	Intermediate (4 weeks):
	 Paper-pencil data collection (+ hospitalization and exacerbation rate) Psychophysiological data collection
	Exit (8 weeks):
	 Paper-pencil data collection (+ hospitalization rate, exacerbation rate credibility/expectancy) Psychophysiological data collection Short exit-interview (telephone)

	Period 2 (follow-up)
	Follow-up 1 (4 months):
	 Paper-pencil data collection (+ hospitalization and exacerbation rate) Psychophysiological data collection Chronic stress (collection of hair sample)
	Follow-up 2 (6 months):
	 Paper-pencil data collection (+ hospitalization and exacerbation rate) Psychophysiological data collection Chronic stress (collection of hair sample) Post-monitoring interview
INTERVENTION	Daily short mindfulness exercises delivered via app
	 App provides 4 audio-files of guided mindfulness exercises Length: 10-15 minutes Mindfulness exercises: Body awareness meditation (Body-scan) Sitting meditation: awareness of the heartbeat Sitting meditation: awareness of the body Sitting meditation: awareness of sounds
	Dose: Patients can choose individually between exercises
	Daily practice: instructions to practice at least once each day, either in the morning or the evening (patients choose in the beginning if they prefer meditating in the morning or in the evening)
	Additional practice: additional meditations are possible and encouraged (it is advised to practice when experiencing respiratory problems, feeling distressed, feeling stressed or whenever considered to be beneficial)
CONTROL	Waitlist control group (receiving treatment as usual during the intervention period)
CONDITION	(same collection of psychophysiological, psychological and biological data, except for the intervention-related measures right before and after the intervention)
INCENTIVES	Weekly "checking-in calls"
CONCOMITANT MEDICATION	Allowed (but must be monitored)

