	For the analysis of the EMA data in the intervention group, multilevel modelling will be used to fit the nested data structure. A two-level model (level 1 = within persons, level 2 = between persons) will be used, with all the assessed subjective variables (e.g. momentary stress) nested on level 1 due to multiple measurements. Pre-post effects of the assessed subjective variables will examine the immediate effects of the MBI.
	Telephone exit interviews will be recorded and analysed using thematic analysis and a mixed methods approach.
DATA	Paper-pencil-data:
MANAGEMENT	• Digitalization: As data are collected on different sites by student research assistants, data will firstly be transported to the Department of Clinical and Health Psychology, University of Vienna, Austria. There, data will be digitalized.

For this process, data will be safely stored in a locked cupboard in the Department of Clinical and Health Psychology, University of Vienna, Austria. Only members of the research team have access to the key.

Klinik Floridsdort

- Final storage of physical data: The study coordinator will transport the physical data safely to the Klinik Ottakring, Vienna, Austria, where the data is finally stored in a locked cupboard. Only members of the research team have access to the key.
- Storage of digital data: Digital data will be stored on the share server of the research team led by [name] [name] (University of Vienna, Austria). A project folder "39 SPIROMIND" was created for the data storage. Each person's access to the folder must be approved by [name] [name] and must be activated by the department's IT team. Only members of the SPIROMIND research team have access to the folder. Additionally, data will be stored on the study coordinator's server of the Klinik Ottakring, Vienna, Austria, and on the study coordinator's server of the Department of Clinical and Health Psychology, University of Vienna, Austria.
- Analysis: Data will be analysed using the software IBM SPSS Statistics, version 24, and the software R, version 3.4.2.

EMA data:

- Access to data: Data are stored on the study's private account of the software MovisensXS. Only members of the research team have access to the account.

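### Pre-post change in the intervention arm alone is read as the exercise's immediate effect, although some sessions are advised when the rated states are raised (minor, secondary outcome)

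*Protocol*

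**What the plan says.** All references are to the Protocol; no SAP is at hand.

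- **Question.** The first secondary research question under Objectives begins "What are the immediate effects of a short mindfulness exercise for stable COPD patients". The Secondary Outcome Variables row files the same ratings under immediate effects.
- **Ratings.** The Methods part of the Executive Summary says that dyspnoea, stress, relaxation, affect and oxygen saturation "will be assessed before and after each exercise via the software". The Measurements row makes them event-based: "pre-meditation (event-based): dyspnea, acute perceived stress" and further items, with a matching set after the exercise.
- **When sessions happen.** The Intervention row asks for at least one session a day, and "patients choose in the beginning if they prefer meditating in the morning or in the evening". Additional sessions are encouraged: "it is advised to practice when experiencing respiratory problems, feeling distressed, feeling stressed or whenever considered to be beneficial".
- **Control arm.** Under Control Condition, the waitlist group has the same data collection "except for the intervention-related measures right before and after the intervention".
- **Analysis.** Statistical Methodology fits a two-level model to the intervention group's EMA data and adds: "Pre-post effects of the assessed subjective variables will examine the immediate effects of the MBI".
- **What is recorded about sessions.** Objectives asks "How often do patients meditate by using the app? How long? When", and about preferred exercises. It does not ask why a session was started.

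**The concern.** Ratings exist only around sessions, and only in one arm, so there are no comparison occasions. For part of the additional sessions, the advice ties the start to respiratory problems, distress or stress. The rated items include dyspnoea, acute stress, anxiety and depression. A state that is high when the session starts tends to be lower a little later, with or without an exercise. A two-level model deals with the nesting of sessions within patients. It does not deal with sessions being selected on the patient's state at the start.

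Read as the plan states it, natural decline can be reported as part of the exercise's immediate effect. The sharper risk is in comparing sessions: symptom-prompted ones would show the larger fall, which could look as if the exercise works best during symptoms. A later analysis plan can add a model term, but it cannot recover a reason that was never recorded.

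**Working it through.** The plan gives no figure for this analysis, so there is nothing to reproduce. The documents supply 15 patients in the intervention arm, 8 weeks (56 days) of daily practice and 10-15 minutes per exercise. Everything else below is an assumption.

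**Model.** The true exercise effect is zero. Ratings have within-person SD 1, pre-post correlation rho and within-person reliability R, with rating errors independent before and after. A prompted session starts when the felt state is more than 1 SD above the patient's own mean. Negative values are falls in an adverse state; relaxation and happiness would move the other way.

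- Mean of the felt state given the trigger: E[z | z > 1] = 0.2420 / 0.1587 = 1.525.
- Expected pre-rating: sqrt(R) x 1.525. The felt state carries over with correlation rho/R.
- Spurious change in prompted sessions: -(1 - rho/R) x sqrt(R) x 1.525.
- Over all sessions: share prompted x that change.

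Example, rho 0.8 and R 0.9: -(1 - 0.8889) x 0.9487 x 1.525 = -0.161. With 20% prompted this is -0.032 overall, with 30% it is -0.048.

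| rho | R | Prompted sessions | All, 20% prompted | All, 30% prompted |
|---|---|---|---|---|
| 0.9 | 0.90 | 0 | 0 | 0 |
| 0.9 | 0.95 | -0.078 | -0.016 | -0.023 |
| 0.9 | 1 | -0.153 | -0.031 | -0.046 |
| 0.8 | 0.80 | 0 | 0 | 0 |
| 0.8 | 0.85 | -0.083 | -0.017 | -0.025 |
| 0.8 | 0.90 | -0.161 | -0.032 | -0.048 |
| 0.8 | 1 | -0.305 | -0.061 | -0.092 |
| 0.7 | 0.90 | -0.322 | -0.064 | -0.096 |
| 0.5 | 0.90 | -0.643 | -0.129 | -0.193 |
| 0.5 | 1 | -0.763 | -0.153 | -0.229 |

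R = 1 is the upper bound for a given rho, trigger and share.

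**Variations.**
- If 30% of sessions are additional but only half of those are symptom-prompted, rho 0.8 and R 0.9 give 0.15 x -0.161 = -0.024 overall and -0.08 for additional sessions as a group.
- If the trigger is a different symptom, correlated k with the rated item, multiply by k.
- If 10-20% of scheduled sessions are also timed to symptoms, scheduled sessions keep -0.008 (rho 0.9, R 0.95, 10%) to -0.06 (rho 0.8, R 1, 20%).

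**Simulation.** This used 2000 trials per setting, 15 patients, 39 scheduled sessions each (70% of 56, assumed) plus 10 or 17 prompted ones, and zero effect. At rho 0.8 and R 0.9, prompted sessions gave -0.16, all sessions -0.033 or -0.049, and scheduled sessions 0 by construction. A separate run fitted a random-intercept model to 56 sessions per patient, 30% of them prompted, with rho 0.7 and selection on the rating itself. It gave -0.14 SD and p < 0.05 in 93 of 100 runs. That run assumed that all patients change alike, so 93% is a high scenario.

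**Bias against standard error.** Let tau be the between-patient SD of the change. Then SE = sqrt((tau^2 + 2(1 - rho)/n)/15), with n sessions per patient.

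- All sessions, rho 0.8, tau 0: SE = 0.023 (n = 49) and 0.022 (n = 56). The bias is 0.033/0.023 = 1.4 to 0.049/0.022 = 2.2 SE.
- With tau 0.3: SE = 0.08, and the bias is 0.4-0.6 SE.
- Prompted minus scheduled, tau 0: SE = sqrt(2(1 - rho)/15 x (1/39 + 1/n)), which is 0.047-0.058 at rho 0.8 and 0.034-0.041 at rho 0.9. The spurious difference is 0.078/0.041 = 1.9 to 0.161/0.047 = 3.4 SE.

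**The case against.** Four points can be made for the plan.

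1. Model terms and interpretive caveats are normally left to the SAP, and the EMA analysis has only a few sentences in a synopsis. This stands for the model term. It does not stand for the causal reading, which Objectives, Secondary Outcome Variables and Statistical Methodology all carry, or for data that must be captured at the session.
2. The app form is not shown and may already ask why a session was started. This stands, so the item is conditional. Time of use and the half of the day chosen in advance help to identify additional sessions, but do not show which of them symptoms prompted.
3. The verb in the analysis sentence is mild, and this is a pilot. That is true, but nowhere is the change described as uncontrolled.
4. The size is unanchored: some plausible inputs give exactly zero, others far more, and with modest variation between patients the overall bias is under one SE. This stands in full. The figures show that the mechanism can matter, not how much it will.

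It is also fair that separating session types is only a partial remedy. Rest, expectancy and natural course remain in every session.

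**Conclusion.** The concern holds, as a minor point. The plan gathers pre- and post-session ratings in one arm only, advises some sessions when the rated states are raised, and reads the change as the immediate effect of the intervention.

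Its size cannot be determined from the documents. With pre-post correlation 0.8-0.9 and 20-30% of sessions prompted, the spurious change over all sessions is 0 to -0.09 SD. At correlation 0.5 with 30% prompted it reaches -0.19 to -0.23 SD. In prompted sessions alone it is larger, and with no exercise effect their apparent advantage over scheduled sessions could lie about 2 to 3 SE from zero if all patients change alike. All of this assumes a trigger at 1 within-person SD and scheduled sessions unrelated to momentary state.

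The randomised comparison on the HADS is not touched.

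**What to change.** 1. Describe the result as uncontrolled within-session change, not as an effect of the exercise, in Objectives, Secondary Outcome Variables and Statistical Methodology.
2. Unless the app form already has it, add one item before each exercise: is this the scheduled daily practice or an additional session, and did symptoms, distress or stress prompt it?
3. Put session type and its interaction with pre/post into the two-level model. Report scheduled and symptom-prompted sessions separately beside the all-session estimate. Do not read a larger fall in prompted sessions as a larger effect.
4. If the item cannot be added, label sessions outside the chosen half of the day, or after the first within it, as additional, and state that this does not show the reason.

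The practice instructions need not change.

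**Cost.** One app item per session, in place before data collection, plus wording and a model term. Patients carry slightly more burden, and the separate estimates are less precise. With the session numbers above, the SE relative to all sessions is sqrt(49/39) = 1.12 to sqrt(56/39) = 1.20 times as large for scheduled sessions and sqrt(56/17) = 1.8 to sqrt(49/10) = 2.2 times for prompted ones if all patients change alike. With tau 0.3 the ratios are 1.01-1.02 and 1.04-1.15. The all-session estimate is kept.
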